- Clinically significant health problems that make projected lifespan \leq 2-years
- LungRads Category 3 or 4 resulted out on screening CT

Recruitment and Consent - Randomized Controlled Trial participants will be recruited through the University of Michigan (200 participants) Health System and the HealthPartners Institute (200 participants).

- At HealthPartners, patients scheduled at HealthPartners Specialty Center will be given an informational flyer and consent form with return envelope during check-in for their Screening CT.
- Patients interested in participating in the study will be asked to contact the study coordinator by telephone within 72-hours (3-days) of their CT scan. During that call the coordinator will review the study requirements, read the consent form to the participant and attest to the patient's willingness to participate in the study. Participant will be asked to mail the last (signature) page of the consent to the coordinator in the envelope provided for back up hard copy.
- Consent forms will specifically request permission to share actual CT images with IMBIO in order to print a Patient Report based on the patient's own CT images. Specific permission will also be sought to share the Patient Report CT screening results with Mayo TTS and the Quitline representative.
- Following the screen, a radiologist will analyze the CT scan image and send the results to the patient's PCP. If the scan is read as a category 1 or 2 in the Lung CT Screening Reporting and Data System (Lung-RADS) [49], patients who have consented to study participation will be randomized to one of four treatment arms. If the scan is read as a category 3, 4A, 4B, or 4X in Lung-RADS the patient will be contacted by their primary care physician's office and told to schedule a follow up appointment. They will be sent a letter informing them they are not eligible for participation in the study after ordering physician has notified them of results and follow-up plans.

Randomization

Upon attestation of consent, eligible participants will be randomly assigned to one of four conditions using a central RedCap database:

1. Usual Care (w/ MN Quitline phone number);
2. Usual Care + Report (w/ IMBIO Quitline number);
3. Usual Care + Counseling; Or
4. Usual Care + Report (w/ IMBIO Quitline number) + Counseling incorporating results of report.

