Those patients randomized to receive the Report will have their radiology images loaded onto a secure flash drive by radiology staff. The images will be uploaded into a HIPAA-compliant web-based portal hosted by IMBIO for processing and generation of the Reports, which can then be downloaded and printed.

Randomization letters, usual care letters and/or reports (Groups 2 & 4) will be mailed to participants. (For participants randomized to Groups 1 & 3, generation and mailing of reports will be delayed until study participation has finished.)

Synopsis of Treatment Arms

Usual Care - Subjects participating in lung cancer screening through HealthPartners and the University of Michigan Health System are referred for screening from their primary care physician (PCP). HealthPartners and the University of Michigan Health System require PCPs to document in the medical order system that current smokers who require a lung cancer screen have been offered smoking cessation counseling prior to providing the screen, in accordance with CMS guidelines [50]. Once a patient is cleared for screening, they are able to schedule an appointment at an affiliated lung cancer-screening site. Following radiologist reading of the scans, eligible study patients randomized to the usual care group will receive a standard results letter in the mail notifying them of screening results with a phone number that will lead them to the state of MN Quitline. The phone number will differ from the MN Quitline number in order to capture calling data. The phone number will provide a short voice message to recipients and then transfer them to the MN or MI Quitline depending on their location.

Tobacco Dependence Counseling

Counseling will consist of one 45-minute session by telephone to occur within two weeks (preferably no more than 10-days) after the lung cancer screen. Counseling sessions will be in accordance with established cessation counseling protocols developed at the Mayo Clinic. Tobacco Treatment Specialists (TTS) will have a complete list of local resources and will facilitate participant enrollment and/or use of medications at the time of the call.

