Outcomes will be assessed at 3 weeks, 3 months, and 6 months. Timing of outcome follow up will begin at time of consent attestation. There will be assessment of participant self-reported use of resources including enrollment in face-to-face cessation programs, calls to quitlines, use of medications, and other smoking cessation services. Participants reporting abstinence at three and six month follow up will be asked to submit saliva cotinine samples to confirm self-reports.

A survey to assess readiness to quit, motivation to make a quit attempt, use of a smoking cessation quitline, quit attempts and long-term smoking abstinence will be developed by [name]. University of Minnesota Office of Measurements Services (Measurement Services) will administer follow up calls to assess readiness to quit, motivation to make a quit attempt, use of a smoking cessation quitline, quit attempts and long-term smoking abstinence. Measurement Services will be blinded to participant's conditions. All participants will receive follow up calls at 3 weeks, 3 months, and 6 months to assess calls to the quitline, readiness to quit, quit attempts, use of cessation aids (programs and medications), as well as current smoking following receipt of their lung cancer screen results.

Given the large number of subjects, Office of Measurement Services will input the survey into the Computer-Assisted Telephone Interviewing (CATI) Software[59] and train staff to ensure a consistent and effective approach.

[name] at the University of Minnesota will manage cotinine analysis. Participants reporting abstinence at 3 and 6 months will be asked to submit saliva samples by mail. A second consent form specific to cotinine collection will be mailed with the collection kit.

All participants will receive \$20 after each of the first and second follow-up calls, and \$70 after the final follow-up call. Participants who report abstinence will be provided an additional incentive of \$50 to provide a saliva sample for a cotinine analysis. A maximum of \$160 will be provided to participants as compensation for their time and as an incentive for their participation. Compensation will be provided as Target gift cards, mailed to patients address on record after confirmation of follow-up completion by University of MN Office of Measurement Services (OMS).

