small. Separate analyses will be performed at each measurement time point (e.g., three-weeks, three-months, and six-months). A similar set of analysis can be performed to assess the main effect of the counseling condition. Logistic and linear models (for the dichotomous and continuous outcomes) with covariates for report condition, counseling condition, and their interaction will be used to assess if the Report and Counseling conditions significantly interact. If the interaction is significant, there will be an examination of whether there is a significant difference between the Report and Usual Care within each level of the Counseling condition. As an exploratory analysis to help guide future studies, a logistic regression model with quit attempt (yes/no) as the response will be utilized. Possible covariates include intervention group, gender, age, number of pack years, interest in quitting at baseline, risk perception at baseline, number of previous quit attempts, and findings from the CT scan, and their interaction with the Report condition. Similar models could be constructed for the other outcomes (abstinence, use of use of smoking cessation services). Additional linear regression models will be constructed for the other outcomes (readiness to quit). Additionally examination will be on whether or not changes in readiness to quit at 3 weeks mediate quit attempts, use of smoking cessation resources, and abstinence at 3 and 6 months using structural equation modeling.

Sample Size: The proposed RCT is powered for a main effects analysis of the Report (averaged over the Counseling condition) for the following outcomes a) at least one 24-hour quit attempt within 6 months of the CT scan b) accessing either formal cessation programs and/or FDA-approved medications within 6 months and c) readiness to quit as measures by the contemplation ladder.

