	5%	15%	15%	25%	81.2%	77.2%	55.1%
Readiness to Quit	6.0	7.5	7.5	9.0	99.9%	97.8%	97.8%
	6.0	7.0	7.0	8.0	93.2%	78.6%	78.6%

the Imbio report and usual CT scan report. Power calculations assume total N=400 and the use of a two-sided test with a 0.05 significance level for the main effect and 0.10 significance level for the effects within each counseling condition level. The power calculation for readiness to quit assume a standard deviation of 2.9 on the contemplation ladder.

Usual Care condition will make a quit attempt (24-hour quit) versus 15% in the Report condition at the time of the 3-week follow-up. The Report will yield significantly greater percentage of subjects reporting a quit attempt at 3 and 6 months.

VII. Title 21 FDA Device Trial Regulations

The IMBIO **Patient Smoking Cessation Report** is currently preparing to undergo the proposed RCT in preparation for eventual FDA approval as a medical device. This trial will be run under the non-significant risk (NSR) section of Title 21 FCR 812.2(b) and will follow the abbreviated trial requirements contained therein. CFR 812.2(b) is uploaded with this application. Also uploaded is Title 21 CFR 56.111, which gives the IRB criteria for approval of NSR clinical device research under the abbreviated requirements associated with FCR 812.2(b).

The IMBIO Patient Smoking Cessation Report, as an NSR device, is not required to seek IDE approval through the FDA prior to starting the clinical trial proposed in this application. IRB agreement that this device qualifies as an NSR device will suffice in lieu of a formal IDE application, as long as said determination of NSR status is transcribed into formal IRB minutes.

This clinical trial will be monitored by the sponsor of the trial, IMBIO, LLC, in accordance with the monitoring requirements found in Title 21 CFR 812.46.

Following the conclusion of the clinical trial proposed in this application, the sponsor will approach the FDA for approval or clearance as a medical device.

VIII. Study Timeline

Phase II Work Plan	2016			2017												2018												2019															
	Oct	Nov	Dec	Jan	Feb	Mar	Apr	May	June	July	Aug	Sept	Oct.	Nov.	Dec.	Jan	Feb	Mar	Apr	May	June	July	Aug	Sept	Oct.	Nov.	Dec.	Jan	Feb	Mar	Apr	May	June	July	Aug.								
Recruit RCT participants																																											
SUBMIT mayo IRB application (with questionnaire developed in SA2)																																											

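### Follow-up is timed from consent, which can precede randomization and delivery of either intervention, so 3-week exposure is undefined and the plan's time origins need reconciling

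*Combined protocol and SAP*

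**What the plan says.** Three time references appear.

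- **Follow-up clock (section V, Data Collection Processes).** "Outcomes will be assessed at 3 weeks, 3 months, and 6 months", and "Timing of outcome follow up will begin at time of consent attestation".
- **Powered endpoint (section VI, Sample Size).** The first outcome is "at least one 24-hour quit attempt within 6 months of the CT scan".
- **Call content (section V).** The list of items for the calls ends with "current smoking following receipt of their lung cancer screen results".

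The order of events is in section IV. Under Recruitment and Consent, interested patients telephone the coordinator within 72 hours of the CT, and consent is attested on that call. If the scan is read as Lung-RADS 1 or 2, "patients who have consented to study participation will be randomized to one of four treatment arms". The Randomization paragraph, however, places assignment of eligible participants at the attestation of consent. For the Report arms, image upload, Report generation, radiologist approval and mailing come next, with no time limit. Counseling is one telephone session "to occur within two weeks (preferably no more than 10-days) after the lung cancer screen".

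Section VI lists 24-hour quit attempts at three weeks among the primary outcome measures and analyzes each time point separately. It expects 5% in Usual Care "versus 15% in the Report condition at the time of the 3-week follow-up", but gives no power for that comparison.

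**The concern.** A quit attempt made before assignment cannot be an effect of the Report or of counseling. Nor can one made after assignment but before delivery be an effect of the Report's content. If such days fall inside the outcome window, both arms accumulate events at the background rate during them and the observed difference shrinks. Over six months a few days hardly matter. Over 21 days they can.

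The 3-week call carries some weight here: it supplies a listed primary outcome, a specific numerical prediction and the readiness measure for the mediation analysis. Separately, call dates, recall questions and the power text do not share one time zero, so it is not clear which attempts count toward the endpoint.

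**Working it through.** **1. The plan's own power figure.** Table 2 gives 98.7% for the Report main effect on 6-month quit attempts. Averaging over counseling gives (20% + 40%)/2 = 30% v (40% + 60%)/2 = 50%, with 200 per group and two-sided alpha 0.05. With the unpooled Wald test:

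- SE = √(0.30×0.70/200 + 0.50×0.50/200) = 0.0480
- power = Φ(0.20/0.0480 − 1.96) = 98.6%

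This reproduces the stated figure. The stated power is not in error.

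**2. Days available at the 3-week call.**

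- *CT to consent:* 0 to 3 days (the 72-hour rule). The CT and consent origins therefore differ by at most 3 days, or 3/182 = 1.6% of six months.
- *Counseling at the 14-day limit:* 11 to 14 days after consent, leaving 7 to 10 of 21 days.
- *Counseling at the preferred 10 days:* 7 to 10 days after consent, leaving 11 to 14 days. Earlier calls leave more.
- *Report:* not computable. The documents give no interval for consent to randomization, for upload and approval, or for mailing.

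**3. Illustration for the Report at 3 weeks.** The assumptions are mine:

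- 5% v 15% is the result of 21 fully exposed days.
- Events accrue at a constant daily rate.
- There is no Report effect for the first d days after consent.
- 5% v 15% applies to the Report main effect, 200 v 200, with no dropout.

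Report-arm rate = 1 − 0.95^(d/21) × 0.85^((21−d)/21). Power = Φ(difference/SE − 1.96), with SE = √(0.05×0.95/200 + p(1−p)/200).

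| Assumed lag d | Report-arm rate p | SE | Power |
|---|---|---|---|
| 0 days | 15.0% | 0.0296 | 92% |
| 3 days | 1 − 0.9927×0.8700 = 13.6% | 0.0287 | 85% |
| 7 days | 1 − 0.9830×0.8973 = 11.8% | 0.0275 | 69% |

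A simpler model, in which the 10-point difference accrues in proportion to exposed days, gives 13.6% and 11.7%, with power of 85% and 68%. The illustration does not depend much on the accrual model. It depends on d, which the plan does not supply.

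**4. The same lag at 6 months.** Applying the same formula to 30% v 50% over 182 days, a 7-day lag gives a Report-side rate of 49.3% and power of 98.1%, against 98.6% with no lag. A 14-day lag gives 97.4%.

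**5. What a randomization origin recovers.** It removes only the part of d that lies before randomization. If, say, 4 days of an assumed 7-day lag came before randomization, 3 days would remain and power would move from 69% to 85%, not to 92%.

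**The case against.** Much of the case on the other side stands.

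- **Consent and randomization may nearly coincide.** The Randomization paragraph assigns eligible participants when consent is attested. If the scan has been read by the time of the consent call, the pre-randomization gap could be close to nil. Days before assignment are possible, not established for every participant.
- **The 15% may already allow for delivery time.** It is stated as of the 3-week follow-up, which runs on the protocol's own clock. The losses above are then upper bounds.
- **Early attempts may not be counted.** If the recall questions are tied to receipt of results, attempts before receipt might not be asked about. The survey is still to be developed, so this is open. A receipt-based window also has a drawback: if a Report were to arrive later than a usual care letter, the window would differ by arm.
- **The differing origins do not cause the loss.** CT and consent are at most 3 days apart, and the receipt wording describes what is asked rather than when. Any loss of sensitivity comes from the lag between consent and delivery. The origins are a separate matter of consistency.
- **Readiness is measured as a state at the call.** Early quit attempts do not accumulate in it, so this calculation does not carry over to the mediator.
- **The trial is not powered on the 3-week quit-attempt comparison.** The powered quit-attempt and service-use endpoints run over six months.

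A reader might infer that the 3-week comparison is mostly diluted, with power falling to about 28%. That figure needs a 14-day lag, which matches the outer limit for counseling, counted from the scan rather than from consent, and not any stated Report delivery time. The documents do not support it. Nor do they support an inference of bias: the clock is common to all four arms and the callers are blinded.

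**Conclusion.** The point holds as a cheap improvement. Follow-up starts at consent, which can precede the scan reading, randomization and delivery, so the 21-day window for a listed primary outcome can include unassigned and untreated days. The randomized comparison is not biased by this. Sensitivity at 3 weeks may be reduced, by an amount the plan leaves undefined; the effect at 6 months is negligible.

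The fall from about 92% to about 85% or 69% rests on assumed lags of 3 and 7 days and on reading 5% v 15% as the effect of full exposure. It is an illustration and an upper bound, not an estimate of the loss in this trial. What the text does establish is that the time references in sections IV, V and VI have to be reconciled.

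**What to change.** 1. Make the randomization date, set once the Lung-RADS 1 or 2 result is known, the single time zero for the 3-week, 3-month and 6-month call dates.
2. Word the recall questions on quit attempts, use of services and smoking as since that date, identically in all four arms.
3. Use the same origin in the Sample Size text in place of the CT scan.
4. Reconcile the two statements in section IV on when randomization occurs with section V and with the sample-size endpoint.
5. Record Report mailing and counseling dates, so that exposure at the 3-week call is known and can be reported. This is needed because the new origin leaves the time from randomization to delivery inside the window.

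The cost is a few wording changes and some date fields in REDCap, which already performs the randomization. Calls fall a few days later. Neither intervention nor its timing changes.

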It is hypothesized that incorporation of the Report into lung cancer screening will improve a patient’s readiness to quit, motivation to make a quit attempt, and increase their use of a smoking cessation quitline and/or other smoking cessation resources including medications. In addition, it is hypothesized that incorporation of the Report into smoking cessation counseling will improve the effectiveness of the behavioral intervention.

Background on Health Belief Model Methodology Incorporated into the Report

Patient-centered Report Design - The Report’s novel image-based design reflects the constructs of the Health Belief Model, widely supported to trigger health-promoting behavior including smoking cessation [38]. The six constructs of the Health Belief Model are listed below with a description of how the Report addresses each construct.

- **Perceived susceptibility** refers to a patient’s belief in the likelihood of getting a disease or condition caused by smoking cigarettes. The Report’s Image section illustrates the patient’s current lung health and

highlights their personal health risk based on information from his or her CT scan. The opportunity to see their own lungs was considered highly interesting and motivating to Phase I study participants. The image engaged the participants and drew them emotionally into the Report. To enhance understanding of the images, the typical colors used in Radiology to indicate healthy lung (dark gray) and disease (red), were discarded in favor of pink to indicate healthy lung tissue and black to indicate disease. The addition of an outline showing a torso to contextualize the lung images greatly improved the participants' comprehension.

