[name], EdD., Treatment Program Coordinator for the Mayo Clinic Nicotine Dependence Center will oversee the coordination and supervision of the Mayo Tobacco Treatment Specialists (TTS). Approximately three TTS will be trained to ensure consistent counseling methodology. TTS follow a validated approach when providing smoking cessation counseling over the phone [51–53]. TTS utilize a patient centered approach grounded in Motivational Interviewing skills [54–58] to elicit perceived benefits for stopping smoking and to enhance self-efficacy for stopping. Specific cognitive and behavioral strategies are collaboratively developed to engage evidence-based strategies for initiating a quit attempt and preventing relapse. A major emphasis of a call is to enroll the caller in formal cessation programs and/or convince them to use FDA approved medication as part of a quit attempt. At the close of each call, TTS confirm that callers are aware of the smoking cessation services available to them. Study participants who desire further smoking cessation support after their 45-minute session will be connected with the appropriate organization: HealthPartners Connect (HP commercial plan), or MN QuitPlan (HP Medicare). Study participants will be strongly encouraged to take advantage of available cessation resources. All participant feedback and questions on the follow up letter and/or Report will be documented. TTS will attempt to reach participants six times on different days and times of day before recording them as non-respondent.

IMBIO Patient Report- Research coordinators at the University of Michigan and HealthPartners will be provided access to Imbio's HIPAA-compliant web portal to upload image data and generate Reports. Following consent and lung screen, research coordinators will manually upload the study participants' images and download a resulting Report which will be mailed to the participants whose treatment arm includes the Report. Radiologists have been designated at both sites to review and approve the Report prior to mailing to participants.

Tobacco Dependence Counseling plus Patient Report- This arm will consist of the mailed report, which the TTS counseling call will incorporate into tobacco cessation discussion.

V. Data Collection Processes-

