Data management - Data will be stored in a secured, centrally located REDCap database. Investigators will oversee the REDCap database setup, data management, audit and edit plans to ensure data accuracy and completeness, and creation of the study's codebook with precise definitions and coding of all variables. A double-checking mechanism will be set up to ensure data completeness and accuracy. Strategies are set up for handling missing data, which are described below.

VI. Data Analysis, Sample Size and Statistics - [name], a biostatistician with the University of Minnesota School of Public Health, will analyze data from the RCT. Similar to standard methods for factorial designs in other therapeutic areas, analyses to address the primary aims will be a test of the main effect of the randomized interventions (i.e., report type and counseling type). All analyses will be by intention-to-treat, and include all participants randomized, regardless of whether they are lost to follow-up. The primary outcome measures will be a dichotomous comparison of 24-hour quit attempts (yes/no) at the time of the three-week follow-up, three-month follow-up, and six-month follow up and subject-reported readiness to quit based on the contemplation ladder among those who have not quit smoking. Secondary outcomes include cotinine-verified abstinence at three and six-months and use of smoking cessation services (dichotomous outcome) at 3 weeks, 3 and 6 months. Initially assessment will focus on the main effect of Report condition (Report vs. Usual Care) averaging or "pooling over" the Counseling condition on the continuous (readiness to quit) and dichotomous outcomes (24-hour quit attempt, abstinence, use of smoking cessation services) using a two sample t-test of the difference in the mean response and two-sided Wald-type test [60] of the difference in proportions, respectively, with a 0.05 significance level. Exact tests (e.g., Barnard's exact test) may be used if the number of successes (e.g., quit attempts, abstinence) is

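### The pooled Report effect does not by itself show that the mailed Report works without a counselor, and the contrast that would show it is reached only through a weak interaction test

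*Combined protocol and SAP*

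**What the plan says.** Section IV (Randomization) lists four arms: (1) Usual Care, (2) Usual Care with the mailed Report, (3) "Usual Care + Counseling; Or" and (4) "Usual Care + Report (w/ IMBIO Quitline number) + Counseling incorporating results of report". The synopsis of treatment arms describes arm 4 as "the mailed report, which the TTS counseling call will incorporate into tobacco cessation discussion". Arm 4 therefore differs from arm 3 in two respects: the document, and the content of the call.

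Section II (Background) gives two hypotheses. One concerns the Report within lung cancer screening. The other is that "incorporation of the Report into smoking cessation counseling will improve the effectiveness of the behavioral intervention".

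Section VI sets the analysis: "Initially assessment will focus on the main effect of Report condition (Report vs. Usual Care", pooled over counseling. Its Sample Size paragraph agrees: "The proposed RCT is powered for a main effects analysis of the Report (averaged over the Counseling condition". Logistic and linear models then test the Report-by-counseling interaction, with no significance level given for that test. Section VI continues: "If the interaction is significant, there will be an examination of whether there is a significant difference between the Report and Usual Care", within each counseling level.

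The Sample Size text also expects Report Only to be significantly better than Usual Care on readiness, quit attempts and use of programs or medication. Table 2 has a power column for that contrast, at the 0.10 level.

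**The concern.** The two Section II hypotheses correspond to two contrasts. Arm 2 v arm 1 isolates the mailed Report. Arm 4 v arm 3 measures the Report plus a call built around it. The primary test averages the two, so a significant result is compatible with a mailed Report that does little alone and a Report-based call that does a good deal.

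The plan separates them only after a significant interaction, and interaction tests in a 2 by 2 design with 100 per arm are weak. The contrast that the plan expects to be significant, and for which it computes power, may therefore never be formally examined. The project's aim is to validate the Report with and without the telephone session (Section I), and the sponsor will approach the FDA after the trial (Section VII). Readers will want to know what the Report does in each setting.

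**Working it through.** **Inputs.** Total N = 400, two-sided 0.05 for the main effect, 0.10 within counseling levels, ladder SD 2.9, and the arm rates, all from Table 2 and its note. Assumed: equal allocation (100 per arm; the ratio is not stated, but this reproduces Table 2), interaction level 0.05, no dropout. Rates are listed as Usual Care / Report Only / Counseling / both.

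**1. Table 2, first row (20/40/40/60%).** Power = Φ(|p2 − p1|/SE − z), unpooled SE.
- Main effect, 30% v 50%, 200 per side: SE = √(0.21/200 + 0.25/200) = 0.0480; 0.20/0.0480 = 4.17; Φ(4.17 − 1.96) = 98.7%. Stated: 98.7%.
- Within level at 0.10, 100 per arm: 93.5% and 89.3%. Stated: 93.5% and 89.3%.

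The other rows agree with Table 2 to within 1 point.

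**2. How often the interaction condition is met at Table 2's own rates.** Logit interaction b = logit(p4) − logit(p3) − logit(p2) + logit(p1); SE = √Σ 1/[100·p(1 − p)].
- First row: b = 0.405 + 0.405 + 0.405 − 1.386 = −0.170; SE = √(3/24 + 1/16) = 0.433; |z| = 0.39; probability of significance about 7%.

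Simulation of four binomial arms (at least 200,000 runs):

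| Outcome and rates | Condition met |
|---|---|
| Quit attempts 20/40/40/60% | 7% |
| Quit attempts 20/35/35/50% | 6% |
| Services 5/17.5/17.5/30% | 15 to 17% |
| Services 5/15/15/25% | 11 to 12% |

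The small ranges reflect how sparse cells are handled. In every row the Report adds the same number of points at both counseling levels. When the condition is met, the cause is chance or the logit scale, not a difference in percentage points.

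**3. Assumed scenarios in which the mailed Report alone does nothing.** These are not rows of Table 2. Arm 2 is set equal to arm 1 and the other arms are left at Table 2's values.
- Quit attempts 20/20/40/60%: b = logit(0.6) − logit(0.4) = 0.811; SE = √(2/24 + 2/16) = 0.456; z = 1.78; Φ(1.78 − 1.96) = 43%.
- Ladder, Report effects 0 and 1.5: SE = 2.9·√(4/100) = 0.58; z = 1.5/0.58 = 2.59; power 73%.

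| Scenario | Pooled test significant | Interaction significant | Pooled significant, interaction not |
|---|---|---|---|
| Quit attempts 20/20/40/60% | 57% | 43% | 33% |
| Services 5/5/17.5/30% | 43% | about 15% | 37% |
| Ladder 0 and 1.5 | 68 to 73% | 73% | 18 to 20% |
| Quit attempts 20/20/40/80% (extreme) | 99% | 96% | 4% |

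The ladder range depends on whether the pooled t-test's SD includes the spread between counseling levels. An intermediate case, quit attempts 20/30/40/60%, gives an interaction probability of about 10%.

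**4. Sensitivity to the interaction level.** At 0.10, the quit-attempt scenario 20/20/40/60% gives 55% interaction power and 25% unflagged. The ladder gives 83% and 12 to 13%. Table 2's own binary rows meet the condition in about 12 to 28% of trials.

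**5. Precision of the stand-alone contrast.** Half-width at 20% v 40%, 100 per arm: 1.96·√(0.16/100 + 0.24/100) = 12.4 points. Pooled: 1.96·0.0480 = 9.4 points. Power of arm 2 v arm 1 at two-sided 0.05:

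| Difference | Power |
|---|---|
| 20% v 40% | about 88% |
| 5% v 17.5% | 80 to 81% |
| Ladder 1.5 | 96% |
| 20% v 35%, 5% v 15%, ladder 1.0 | 66 to 68% |

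**The case against.** A reader might infer that a positive pooled result cannot be credited to the Report at all, or that a factorial main effect is valid only if the factor is the same treatment at both levels of the other. Neither follows. The Report is randomized and counseling is assigned on both sides of the Report margin. A call that discusses the Report is an intended consequence of having one, and Section II hypothesizes it. A main effect is an average over the levels of the other factor and needs no equality between them. Section VI chooses that average openly and powers it. This part of the objection stands in full.

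It can also be said that the plan names the stand-alone contrast, expects it to be significant and gives its power. That is so, and it makes the condition harder to justify: the analysis text does not schedule unconditionally what the Sample Size text expects.

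On size, the zero-effect scenarios are assumptions, the interaction level is not stated, and the largest unflagged rate is for services, which Section VI lists among the secondary outcomes although the Sample Size text powers it. The ladder fares better, and an extreme interaction is nearly always detected. These limits are fair, but the result at Table 2's own rates does not depend on any zero-effect scenario.

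Finally, the documents state no stand-alone device claim. Any harm from misreading the pooled result is a possibility, not something the plan commits to.

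**Conclusion.** The concern holds in limited form. The pooled test is sound for the Report as delivered, averaged over counseling. Alone, it does not show that the mailed Report works without a counselor.

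The weakness is the condition placed on the within-level contrasts. Assuming 100 per arm and an interaction level of 0.05, it is met in only about 6 to 17% of trials if Table 2's binary rates are right. If the mailed Report alone had no effect, it is met in about 43%, 15% and 73% of trials for quit attempts, services and the ladder, in the scenarios shown.

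The matching unflagged rates of 33%, 37% and 18 to 20% might be read as false-positive rates. They are not: in each scenario the pooled effect is real, and what goes unnoticed is where it comes from. This is a cheap improvement to the analysis plan, not a flaw in the design or the primary test.

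**What to change.** In Section VI:
- Keep the pooled Report main effect as the primary test.
- Remove the requirement of a significant interaction. Always report Report Only v Usual Care and Report + Counseling v Counseling, with 95% intervals, beside the pooled effect. The interaction estimate can stay as a description, with its significance level stated if it is tested.
- Link the two Section II hypotheses to these two contrasts.
- Describe the pooled result as the effect of the Report as delivered, averaged over counseling. Base any statement about the Report on its own on Report Only v Usual Care.

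The cost is wording and two contrasts on data already collected, with no extra participants. The downside is precision. The stand-alone interval is about ±12 points against ±9 pooled at Table 2's first row. Power at two-sided 0.05 is adequate for the differences that the plan calls of interest but only 66 to 68% for Table 2's smaller ones. A non-significant stand-alone result should therefore be read from its interval and not taken as evidence of no effect.
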